- b) examine whether the reduction of drinking in phase 1 initial 12-week treatment responders (defined as ≥60% reduction in drinks/wk during weeks 9-12) can be maintained in a 12-week double blind phase 2 extension of the initial treatment condition to help identify the clinical utility of dutasteride as a treatment for AUD, which is a chronic relapsing disorder;
- **c)** examine whether pbo arm non-responders during phase 1 experience a reduction in drinking when crossed over to dutasteride during the 12-week phase 2 extension; and **d)** examine the moderating effects on treatment outcomes of baseline self-reports of drinking to cope, trait anxiety, perceived stress, adverse child experiences and a polymorphism (rs1360780) in the *FKBP5* gene encoding a key chaperone protein regulating functions of androgen, progesterone and glucocorticoid receptors that has been

associated with negative behavioral responses to life stressors, including increased heavy drinking in college students (Lieberman, Armeli et al. 2016) and a stronger linkage between drinking to cope and next day emotional depletion.

Specific Aims.

Aim 1. To examine the safety, tolerability and efficacy of dutasteride in helping patients with AUD to reduce or stop drinking, 190 treatment-seeking men and women with AUD who drink heavily on a regular basis (\geq 24 standard drinks / week for men and \geq 18 drinks/week for women) will be randomly assigned to treatment with either dutasteride or pbo for 12 weeks. A biological marker (PEth phosphatidylethanol) will be used as a secondary measure of change in alcohol use and the dihydrotestosterone (DHT) metabolite 3α -androstanediol glucuronide will be used to monitor dutasteride inhibition of 5α -reductase enzyme activity. We hypothesize that dutasteride 1 mg/day will be well tolerated by both male and female heavy drinkers, will produce \geq 80% reduction in the serum marker of 5α -reductase enzyme activity and will result in a greater reduction in the number of heavy drinking days and drinks per week than pbo and that treatment effects will be greater for women as they are expected to more frequently experience drinking to cope, higher anxiety and a history of childhood adversity/trauma.

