We recently completed the first RCT of **Dutasteride for the reduction of heavy** drinking in men. Results support further examination of dutasteride as a treatment option for AUD. In total 189 treatment seeking men were enrolled of which 24 were screen failures and 23 failed to return for the baseline visit leaving 142 subjects randomized to medication (dutasteride n=74). Seven subjects did not return after the baseline randomization visit providing a modified intention to treat sample of 135 subjects (68 dutasteride and 67 placebo) who provided drinking data post-randomization. One hundred seven subjects completed the entire 12-week treatment. The mean number of treatment weeks completed were not different between arms (dut 10.2 vs. pbo 10.7). 3α androstanediol glucuronide levels were decreased by 80% in the dutasteride group at both 6 and 12 weeks vs. 0% in pbo treated subjects confirming the anticipated pharmacological effect for our study design. There were no significant differences between groups (dutasteride vs. pbo) for measures of alcohol consumption during the 60-days prior to screening including the number of standard drinks (SD) per week (48.8 vs. 47.3), number of heavy drinking days (HDD, 5 or more drinks for men) per week (5.2 vs. 5.2), or abstinent days per week (0.67 vs. 0.62). While the dutasteride group were more likely to have had a prior episode of treatment for alcohol use (59% vs. 40%, p=0.03) the number of DSM-IV AD criteria did not significantly differ between groups (4.3 vs. 4.0).

[figure not shown]
Safety. There were no study related serious adverse effects. The proportion of subjects exposed to study medication who reported at least one non-serious adverse

[figure not shown]
effect was not significantly different for the dutasteride vs. pbo groups 71.6% vs. 67.1% similarly, the number of side effects per subject was not different between dutasteride and placebo groups, 1.36 ± 1.46 vs. 1.03 ± 1.10 . Adverse events that were reported by more patients in the dutasteride compared with the placebo arm included stomach discomfort (16.4% vs. 4.5%, p=0.04) and reduced libido (9.0% vs. 0%; p=0.03). More subjects in the dutasteride arm (n=4) than the pbo arm (n=1) stopped medication due to side effects. Beck Depression Inventory scores were low in both treatment arms at baseline (10.4 dut vs. 7.5 pbo) and reduced to a similar degree during the 12-week treatment (-3.3 dut vs. -2.4 pbo, t=0.6; p=0.5).

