We did not exclude subjects with concomitant use of medications for anxiety or depression, 20% of subjects were taking such medications at baseline. Patients in the high DTC group were more likely to take medication for anxiety or depression than the low DTC group 28.3% vs. 12.5% [χ^2 =4.2, p=0.04; OR = 2.7].

Figure 3. Mean drinks per week contrasting subjects taking or not taking concominant medications for anxiety or depression stratified by placebo (left) vs. dutasteride treatment (right). The standard error of the mean is represented.

Reductions in drinks per week among dutasteride treated subjects was not impacted by concurrent medication use for anxiety or depression (Fig 3 right), while among placebo subjects there were very limited reductions in drinking for subjects taking medication for anxiety or depression compared with placebo treated subjects without ongoing use of such medications (SD/wk F=7.8, df=1,596, p=0.005), Fig 3 left.

Summary: Results from the first study of dutasteride for AUD conducted in men indicate that dutasteride is well tolerated and significantly reduced alcohol use compared with placebo in moderate to heavy drinkers. Further, dutasteride-treated subjects with elevated baseline self-reported DTC motives and anxiety showed the largest reductions in drinking compared with placebo. Drinking to cope with negative affect and anxiety are common clinical challenges in the treatment of AUD (Smith and Randall 2012) (Menary, Kushner et al. 2011, Crum, Mojtabai et al. 2013). These results suggest that dutasteride may have particular benefit for patients with these characteristics. The associations of dutasteride response with baseline measures related to stress suggest that the effects of dutasteride to reduce drinking may include a mechanism of action involving the HPA stress response system.

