2.C.8 Exploratory microbiome analysis Leclercq et al (Leclercq, Matamoros et al. 2014, Leclercq, de Timary et al. 2017) have reported that as many as 40% of alcohol dependent subjects may harbor pro-inflammatory gut microbiota contributing to increased gut permeability which was associated with higher anxiety and alcohol craving after 3 weeks of abstinence. Our hypothesis is that participants with higher levels of pro-inflammatory gut microbes at baseline will have less success in reducing drinking. Stool samples will be collected by participants at home and transported to the CRC in a small cooler with freezer packs. Samples will be stored at -80C until batch processed. DNA will be prepared from stool samples and used for metagenomics whole genome shotgun sequencing of microbial DNA. This method allows species and strain level identification of the gut microbiome. Analysis of sequence data and comparison of strains by treatment response will be done by [name] Assistant Professor of Medicine at UConn Health who is an experienced investigator in molecular characterization of human microbiomes. Correlations of the relative abundance of microbes in baseline stool samples with participant success and in reducing weekly drinking will be examined. We will also examine change in microbiome between baseline and endpoint as a function of change in drinking.

2.C.9. Data Analysis:

2.C.9.a.1. Safety: Safety will be analyzed using categorical outcomes, defined by the type and severity of adverse effects. Summary measures of adverse effects (AEs) will be developed by organ system from the SAFTEE adverse event checklist and will be compared for patients receiving dutasteride or pbo using χ^2 analysis in phase 1 and

comparing patients switched to dutasteride vs. naltrexone in phase 2. Comparisons will be conducted on 1) the proportion of patients in each of the comparison groups who report AEs, 2) the proportion of patients in each of the comparison groups who report moderate-to-severe AEs, and 3) the proportion of patients in each comparison group who discontinue treatment due to AEs. Individual AEs that occur in \geq 5% of patients in either medication condition will be examined using χ^2 analysis.

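### Aim 1 claims tolerability in both sexes, but the planned phase 1 safety analysis is pooled χ² tests with no effect estimate, interval or comparison by sex

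*Combined protocol and SAP*

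**What the plan says.** Specific Aims, Aim 1: "We hypothesize that dutasteride 1 mg/day will be well tolerated by both male and female heavy drinkers". No rate, margin or other criterion for tolerability is attached.

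Section 2.C.9.a.1 (Safety): summary measures by organ system from the adverse-event checklist "will be compared for patients receiving dutasteride or pbo using χ^2 analysis in phase 1". Three proportions are named: any adverse event (AE), moderate-to-severe AE, and "the proportion of patients in each comparison group who discontinue treatment due to AEs". Individual AEs seen in at least 5% of either arm also get a χ² test. In phase 2 the comparison is between patients switched to dutasteride and patients switched to naltrexone. The section has no effect estimate, no interval and no analysis by sex.

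Section 2.C.9.b (Sample size considerations) covers drinking outcomes only. The one non-inferiority margin, in 2.C.9.a.2, concerns drinking in dutasteride responders.

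Section 2.B.2 (Preliminary studies) reports the first trial, in men. The share with at least one non-serious adverse "effect was not significantly different for the dutasteride vs. pbo groups 71.6% vs. 67.1"%. It also says: "More subjects in the dutasteride arm (n=4) than the pbo arm (n=1) stopped medication due to side effects". Two individual AEs were significantly more frequent on dutasteride: stomach discomfort (16.4% vs 4.5%, p=0.04) and reduced libido (9.0% vs 0%, p=0.03). The summary of that section concludes that "dutasteride is well tolerated and significantly reduced alcohol use compared with placebo".

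**The concern.** To call a drug well tolerated is to say that it causes no important excess of harm. A difference test addresses the opposite question. It can reject equality of the arms, but failing to reject says little unless one knows which excesses the data exclude, and only an interval shows that. If the χ² results are all the report contains, a p-value above 0.05 may be read as support for the hypothesis whether or not a relevant excess exists.

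The gap is widest for women. They are named in the hypothesis and had no place in the first trial. They are expected to be only 35% of the sample (section 2.C.2), and the safety section sets out no comparison within them. Efficacy, by contrast, has a planned sex-by-treatment interaction (2.C.9.a.2).

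**Working it through.** The documents give no power, margin or expected width for any safety comparison, so there is no safety figure to reproduce. The question is what the planned test can and cannot show.

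**Inputs**

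- Arm size: 95 (Table 1, section 2.C.1). Women per arm: 0.35 × 95 = 33.25, taken as 33.
- First-trial stops for side effects: 4 dutasteride, 1 placebo. The denominators for these counts are not stated. I assume all randomised: "leaving 142 subjects randomized to medication (dutasteride n=74"), which leaves 142 − 74 = 68 on placebo. The rates are 4/74 = 5.4% and 1/68 = 1.5%.
- Other first-trial rates as listed above.
- Assumed test: uncorrected Pearson χ², two-sided 0.05.

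**Miss rate.** For a stops on dutasteride and b on placebo, n per arm, and p̄ = (a+b)/(2n):

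X² = (a/n − b/n)² / [p̄(1−p̄)(2/n)]

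Miss rate = sum of Bin(a; n, p_D) × Bin(b; n, p_P) over all (a, b) with X² ≤ 3.84.

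| First-trial rates, dutasteride vs placebo | Missed, 95 per arm | Missed, 33 women per arm |
|---|---|---|
| Stopped for side effects, 5.4% vs 1.5% | 70% | 94% |
| At least one AE, 71.6% vs 67.1% | 90% | 93% |
| Stomach discomfort, 16.4% vs 4.5% | 20% | 62% |
| Reduced libido, 9.0% vs 0% | 2% | 65% |

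**Sensitivity of the first row at the overall size.** With the modified intention-to-treat denominators (4/68 vs 1/67) the miss rate is 66%. With 80 completers per arm it is 75% (randomised denominators) or 71% (modified intention-to-treat). With Yates-corrected χ² or Fisher's test the four cases run from 80% to 89%.

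**How firm the 4 vs 1 figure is.** The difference is 5.41 − 1.47 = 3.94 points. The Wilson limits are 2.12% to 13.09% and 0.26% to 7.87%. Newcombe's interval combines them:

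- lower = 3.94 − √[(5.41−2.12)² + (7.87−1.47)²] = −3.3 points
- upper = 3.94 + √[(13.09−5.41)² + (1.47−0.26)²] = +11.7 points

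The χ² p-value is 0.20. The excess is compatible with zero and with nearly 12 points.

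**What χ² alone would hide in this trial.** Suppose 6/95 against 1/95 stop. Then X² = 3.71 and p = 0.054, which is not significant. The difference is 5.26 points. With Wilson limits of 2.93% to 13.10% and 0.19% to 5.72%, Newcombe's interval is −0.5 to +12.1 points. A seventh dutasteride stop gives X² = 4.70, p = 0.030.

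**What an interval would show in women.** Even with no stops among 33 women in each arm, the Wilson upper limit for each arm is z²/(n+z²) = 3.84/36.84 = 10.4%. The Newcombe interval for the difference is then −10.4 to +10.4 points.

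**The case against.** A reader might infer that the protocol makes non-significance the criterion for tolerability. The documents do not say so. Section 2.C.9.a.1 lists comparisons and no decision rule. The first trial's report shows that the judgement did not require every test to be non-significant: it set out two significant AE excesses and the 4 vs 1 stops, noted no study-related serious events, and still called the drug well tolerated. That part of the objection stands.

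A reader might also infer that the trial would generally miss harms of the size already seen. That too goes beyond the figures. The low power concerns discontinuation and the overall AE rate, while the two individual AE excesses would usually be detected in the full sample. The discontinuation rates rest on five events. The figures for women apply rates from men to a test that the plan does not include.

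The protocol has other safety information: depression and anxiety scales, the PHQ-9 at every visit, the phase 2 comparison and semi-annual review by the monitoring board. These protect participants and inform judgement. None of them gives an estimate with an interval for dutasteride against placebo, and the phase 2 comparator for switched patients is naltrexone.

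Finally, one could demand a tolerability margin. The trial was not sized for one. With 95 per arm and a Newcombe upper limit, a 5-point discontinuation margin would be met only about 55% of the time by a drug with no excess (1.5% in both arms). A 10-point margin would be met about 45% of the time by a drug truly at 5.4% against 1.5%. A margin is a trade-off, and its absence is not an error.

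**Conclusion.** The point holds in a limited form. The protocol states a tolerability hypothesis for both sexes and plans, for phase 1, only pooled difference tests, which cannot support it when they are non-significant. The documents leave open how tolerability will be judged, so a conclusion drawn from p>0.05 is a risk that the plan does not guard against.

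The size is illustrative. The discontinuation miss rate of about 70% overall assumes the first trial's rates, all-randomised denominators and an uncorrected two-sided χ² test at 0.05. Other reasonable choices of denominator, arm size and test give 66% to 89%. The figure of about 94% for 33 women per arm also assumes that rates in men carry over to women. Neither figure shows that dutasteride causes such an excess. Since first-trial data leave anything from −3.3 to +11.7 points open, estimates with intervals are more useful here than p-values.

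**What to change.** In section 2.C.9.a.1, for any AE, moderate-to-severe AE and discontinuation due to AE:

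- report the phase 1 dutasteride-minus-placebo risk difference with a two-sided 95% confidence interval (for example Newcombe), overall and separately for women and men;
- base the statement on tolerability on the estimate and on the largest excess that the interval does not rule out;
- state that p>0.05 will not be taken as evidence of tolerability;
- keep the χ² tests, including those of individual AEs, as descriptive screening.

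A pre-specified margin is optional. If the investigators want one, its value is theirs to choose and should be fixed before unblinding.

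The cost is a few sentences and no new data. The tolerability statement will become more cautious, above all for women, where the intervals will be wide.

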comparison in phase 1 and a within-subjects test in phase 2 for patients treated with pbo in phase 1 and dutasteride in phase 2, iii) allow evaluation of whether reductions in drinking are maintained with ongoing treatment for phase 1 dutasteride responders, and iv) provide preliminary data on whether dutasteride non-responders show reductions in drinking when crossed over to naltrexone, an established medication for AUD with a different mechanism of action compared with dutasteride.

Three and six-month follow-up visits following the completion of the 24-week treatment phase will evaluate the durability of treatment effects, allow measurement of the degree to which dutasteride effects on 5AR inhibition have been reversed following 12- or 24-week exposures and to maintain contact with female participants to remind them of the importance of effective contraception for 6 months following treatment.

Table 1. Expected Patient Distribution for Phase 1 and 2.

Phase 1	Phase 1	Phase 1	Phase 2	Phase 2 Statistical contrasts
Treatment	Statistical	Expected Tx	Treatment	
	contrasts	response groups		
Dutasteride n=95 (grp A)	Between-subject contrasts using GLMM Dut vs. Pbo for DVs HDD/wk and SD/wk;.	Dut-R (wk 9-12 Response n=40) Dut-NR (wk 9- 12 Non-Response n=40)	Dut-R dutasteride Dut-NR naltrexone	Within-subject interrupted time series regression using mixed models. Dut-R: Is dut response maintained? Dut-NR: Do dut NRs respond to naltrexone?
	Moderating			
Pbo n=95 (grp B)	effects of genotype, baseline state vs. trait anxiety, perceived stress and interaction with FKBP5 genotype	Pbo-R (wk 9-12 Response n=16) Pbo-NR (wk 9- 12 Non-Response n=64)	Pbo-R pbo Pbo-NR dutasteride	Pbo-R: insufficient sample for statistical comparison. Pbo-NR: Do pbo NRs respond to Dut?

Phase 1 response ≥ 60% reduction SD/wk for wk 9-12 vs baseline (current study 49% response rate for dut vs. 20% pbo). dutasteride 1 mg/day; naltrexone 50 mg/day.

2.C.2. Patients: Drinkers who want to reduce or stop drinking will be recruited using advertisements in radio and print media, by posting/distributing recruitment materials in community settings, informational mailings to area clinicians and by referral from UConn Health medical and dental clinics in at our main campus in Farmington CT together with

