2.C.3.a. Dutasteride is FDA approved to treat prostatic hypertrophy and is a competitive and specific inhibitor of both type I and type II steroid 5α-reductase enzymes with which it forms a stable enzyme complex with very slow dissociation. In humans, type I 5AR is present in the brain, liver, adrenal gland, and adipose tissue and is responsible for onethird of circulating DHT. Type II 5AR is present in the liver and prostate, and is responsible for two-thirds of circulating DHT. For studies of alcohol use, inhibition of type I 5AR may be of particular importance, as type I 5AR, but not type II enzyme, is present in the adult brain (Lephart, Lund et al. 2001) where local generation of neuroactive steroids is thought to occur in addition to peripherally generated neuroactive steroids. The dutasteride dose of 1 mg/day proposed for this study is expected to achieve a >90% inhibition of peripheral type II 5AR and a 60% inhibition of type 1 5AR by 4 weeks for a total reduction in DHT of ≅ 80% by 4 wks based on pharmacokinetic models (Gisleskog, Hermann et al. 1998) and consistent with our observed 80% reduction in 3α-adiol glucuronide at 6 wks in our recently completed initial study in men using this dose. Dutasteride will be purchased commercially and over encapsulated using opaque capsules by the UConn Health Research Pharmacy Service. Pbo will be formulated to match the active medication. Subjects will take one 0.5 mg capsule of dutasteride or matching pbo during the first

treatment visit (baseline study visit 2) and at home on day 2 followed by two capsules daily for either 12 or 24 weeks (depending on treatment response). Similarly, subjects transitioning from placebo or dutasteride based on phase 1 non-response will be given one capsule of medication (dutasteride 0.5 mg or naltrexone 25 mg) during their first phase 2 study visit and day 2 of phase 2 followed by two capsules daily for 12 weeks.

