- 2.C.3.d. Medication Randomization and Drug Accountability: Urn randomization (Stout, Wirtz et al. 1994) will be used to assign subjects 1:1 to dutasteride or pbo for treatment phase 1, balancing for number of DSM5 AUD criteria (2-5 vs.>5), DTC relative to total motives score (0-25% vs. >25%), *FKBP5* genotype (CC vs. T-carrier), current smoking status, and use of medication for treatment of co-morbid psychiatric condition. Separate

randomizations will be done for women and men to ensure balance on these variables in both sex groups. At the end of phase 1, patients who have reduced drinks/week by at least 60% will continue for the second 12 wks on the originally randomized treatment taking 2 capsules per day. Subjects who have reduced drinks/wk by less than 60%, will be informed that they will be transitioning to an active study medication (either dutasteride or naltrexone), and will be interviewed to confirm they have not used opioid medication for 5 days prior which will be verified by urine testing, subjects testing positive for opioids will not be eligible for starting phase 2. For non-responder subjects in the phase 1 pbo arm, the pharmacy will begin dispensing 0.5 mg dutasteride capsules with instructions to take 1 capsule per day for 2 days, then 2 capsules daily for 12 weeks. For subjects in the initial dutasteride arm and reducing less than 60%, the pharmacy will dispense 25 mg naltrexone capsules with the same instructions of 1 capsule for days 1 and 2 followed by 2 capsules each day (50 mg naltrexone per day) to match the dutasteride capsule dosing. Medication vials including any unused medication will brought to each follow-up visit. Unused pill counts will be recorded by the study nurse at each bi-weekly visit and medication use recorded daily by patients on their drink log.

2.C.4. Study Visits:

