dutasteride arm non-responders switched to naltrexone to determine whether naltrexone is effective in reducing drinking in dutasteride non-responders. An interrupted time series regression using mixed models will be used (Wagner, Soumerai et al. 2002, mallinckrodt and Lipkovich 2017), where in addition to a variable for week an indicator variable for phase, a second weekly variable that is sequentially coded beginning at phase 2 and the interaction of the two variables will be included in the model. The phase indicator variable will measure change when entering phase 2 and the second weekly variable will measure change in trajectory deviating from phase 1. In addition, a restricted period analysis focusing on the average of the last 4 weeks of phase 1 compared to average of the last 4 weeks of phase 2 will be conducted. This may be more sensitive if the first few weeks of each phase show limited initial response, which would dilute the effects for phase and the interaction for the interrupted regression model. For the first group, dutasteride responders, a non-inferiority test will be used where the non-inferior margin will be 20% above the drinking levels during phase 1. For the latter two groups of non-responders a superiority test will be used.

For aim 3, analysis of drinking outcomes will be repeated including baseline measures of DTC, trait anxiety, perceived stress, adverse child event count and genotype for the *FKBP5* rs1360780 SNP (CC vs. T-carrier) as additional between-subject factors together with the 2- and 3-way interactions of medication condition with DTC, SAI, PSS or ACES measures and *FKBP5* genotype. We will include both Blacks and Caucasians in the pharmacogenetics analysis as our prior study showed similar interactions of *FKBP5* genotype with life stress on drinking measures in both Black and Caucasian college students (Lieberman, Armeli et al. 2016).

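### The Phase 2 adverse-event comparison sets patients newly on dutasteride against a non-randomised naltrexone group that has just finished 12 weeks of dutasteride, so it should be descriptive and leave the safety inference to Phase 1.

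*Combined protocol and SAP*

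**What the plan says.** Section 2.C.9.a.1 (Safety) has AE summaries "compared for patients receiving dutasteride or pbo using χ^2 analysis in phase 1" and, in the same sentence, "comparing patients switched to dutasteride vs. naltrexone in phase 2". The comparisons cover any AE, moderate-to-severe AEs and discontinuation for AEs. Individual AEs reaching 5% in either medication condition are also tested by chi-square. The sentence names chi-square beside Phase 1; no other method is given for Phase 2, so the natural reading is that the same test applies.

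How the Phase 2 groups arise is set out in section 2.C.3.d. Urn randomisation "will be used to assign subjects 1:1 to dutasteride or pbo for treatment phase 1"; nothing is randomised at week 12. The placebo side is described thus: "For non-responder subjects in the phase 1 pbo arm, the pharmacy will begin dispensing 0.5 mg dutasteride capsules". The dutasteride side: "For subjects in the initial dutasteride arm and reducing less than 60%, the pharmacy will dispense 25 mg naltrexone capsules". Table 1 expects 64 and 40 patients.

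Section 2.C.3.a has the new drug given at the first Phase 2 visit. The transition conditions in 2.C.3.b and 2.C.3.d concern opioids only. On persistence, 2.C.3.a says that dutasteride "forms a stable enzyme complex with very slow dissociation", and 2.C.1 uses the 3- and 6-month follow-up visits to see how far its effects on the enzyme "have been reversed following 12- or 24-week exposures". Section 3.A.3 sets precautions for 6 months after stopping.

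For efficacy, 2.C.9.a.2 analyses the same naltrexone group "to determine whether naltrexone is effective in reducing drinking in dutasteride non-responders".

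**The concern.** A test between two groups reads as a drug comparison, and this one differs from that in three ways.

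- **Selection.** Each group is defined by original arm plus a post-randomisation outcome, with expected non-response of about 50% on dutasteride and 80% on placebo. No adjustment is planned.
- **Prior exposure.** One group is new to dutasteride. The other has just had 12 weeks of it.
- **Counting.** Side effects are recorded by SAFTEE at every bi-weekly visit (2.C.6.b.4), but no rule says whether an AE that began in Phase 1 and continues counts in Phase 2.

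At stake is how the 64 added dutasteride exposures are read. Aim 2B exists partly to increase the number of patients treated with dutasteride under double-blind conditions. A non-significant Phase 2 result could be reported as reassurance when the contrast had little chance of showing anything.

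**Working it through.** **Inputs.** Group sizes 64 and 40 (Table 1). Prior-trial AE rates, dutasteride vs placebo (2.B.2): reduced libido 9.0% vs 0%, stomach discomfort 16.4% vs 4.5%. Naltrexone nausea 10% (3.A.3). Two-sided alpha of 0.05 is assumed, because 2.C.9.b states alpha for efficacy only. No power is stated for any safety test.

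**Reproducing the plan's figures.** With 80 completers per arm and response rates of 49% and 20%, non-responders number 80 × 0.51 = 40.8 and 80 × 0.80 = 64.0, matching Table 1. For the AE rates, assumed counts of 11/67 vs 3/67 and 6/67 vs 0/67 give Fisher p-values of 0.045 and 0.028, consistent with the stated 0.04 and 0.03.

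**Carry-over model.** Let c be the share of the dutasteride AE excess that persists and is counted in Phase 2. The rate in the naltrexone group, before any effect of naltrexone itself, is

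p_nal = p_pbo + c × (p_dut − p_pbo).

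The documents give no value for c, so the whole range from 0 to 1 is shown. Power is the summed binomial probability of all outcomes (a of 64, b of 40) for which the uncorrected chi-square, (a/64 − b/40)² / [p̄(1 − p̄)(1/64 + 1/40)], exceeds 3.84.

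| AE | c | Comparator rate | Difference (points) | Exact power |
|---|---|---|---|---|
| Reduced libido | 0 | 0% | 9.0 | 52% |
| | 0.5 | 4.5% | 4.5 | 11% |
| | 1 | 9.0% | 0 | 4% |
| Stomach discomfort | 0 | 4.5% | 11.9 | 45% |
| | 0.5 | 10.45% | 5.95 | 12% |
| | 1 | 16.4% | 0 | 5% |

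At c = 1 the figure is just the test's false-positive rate.

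**Naltrexone's own AEs.** Suppose its 10% nausea adds independently to stomach discomfort (an assumption). The comparator rate becomes 1 − (1 − p_nal) × 0.90, and dutasteride minus naltrexone is:

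- c = 0: 16.4 − 14.05 = +2.35 points
- c = 0.5: 16.4 − 19.4 = −3.0 points
- c = 1: 16.4 − 24.8 = −8.4 points

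The sign can change.

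**Early leavers.** If half of those with reduced libido had left during Phase 1, the rate among those remaining would be 0.045 / (1 − 0.045) = 4.7%. The difference at full carry-over would then be 9.0 − 4.7 = 4.3 points instead of 0. This weakens the attenuation but does not reverse it.

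**Phase 1 for comparison.** The same enumeration with 95 per arm at the prior-trial rates gives 98% power for libido and 80% for stomach discomfort.

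**The case against.** **The randomised Phase 1 comparison already covers these events.** This stands. Phase 1 is free of carry-over, is better powered, and is where Aim 1 places safety. A reader might infer that dutasteride's libido and stomach effects would be masked in the trial; they would not be.

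**The direction of bias is not fixed.** This also stands. A reader might infer that the Phase 2 contrast must lean toward no difference. The documents show persisting enzyme inhibition, not persisting side effects. SAFTEE is described as covering treatment-emergent effects and is given at week 12, so counting only new onsets would remove most carried-over events. Naltrexone has AEs of its own, and selection by response has no sign that the documents determine.

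**The baseline for the loss must be realistic.** A reader might measure the loss for stomach discomfort from a comparator rate of 0%, where power would be 96%. The prior placebo rate was 4.5%, so the no-carry-over figure is 45%.

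**The paired alternative gains little.** For libido, with no events on placebo, exact McNemar needs at least 6 of 64 patients with an event. At 9.0% that has probability 52%, the same as chi-square without carry-over. It also brings time effects and selection on placebo non-response. What it does remove is the dutasteride-exposed comparator.

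**The naltrexone arm is modest in ambition.** Section 2.C.1 calls it preliminary, and its efficacy question is confined to dutasteride non-responders. That leaves only a caveat of wording on efficacy.

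**Conclusion.** The point holds for the Phase 2 AE comparison only. As written, the plan tests two non-randomised groups, one of them directly off 12 weeks of dutasteride, with no adjustment and no onset rule. The result cannot be read as dutasteride against naltrexone, and a null result would say little. Even without carry-over, power is only 52% for libido and 45% for stomach discomfort. At half persistence it falls to about 11% and 12%, and at full persistence to the false-positive rate.

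These figures assume the Table 1 group sizes, the AE rates of the prior trial (men only), a two-sided 0.05 test, and carry-over shares that the documents do not supply. The table also leaves out naltrexone's own AEs, which can turn the contrast in dutasteride's favour. The documents support neither a fixed direction of bias nor a flaw in the Phase 1 safety analysis. The consequence for the naltrexone efficacy result is a minor caveat of interpretation.

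**What to change.** Amend 2.C.9.a.1 as follows:

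1. State that the dutasteride safety inference rests on the randomised Phase 1 comparison.
2. Present the Phase 2 dutasteride and naltrexone AE table as descriptive and non-randomised, without a test.
3. Count in Phase 2 only AEs that start or worsen after the switch.
4. Add a within-patient comparison of placebo-to-dutasteride patients with their own Phase 1 placebo period (McNemar). State its limits: time effects and selection on Phase 1 non-response.
5. Report 3-alpha-diolG at weeks 18 and 24 in the naltrexone group, and word the naltrexone result in 2.C.9.a.2 as a switch with possible residual 5-alpha-reductase inhibition.

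The cost is some SAP wording, one paired table and one laboratory summary. SAFTEE is already scheduled at each visit, and 3-alpha-diolG is already collected at weeks 18 and 24 (2.C.6.a). No visit, dose or transition procedure changes. The price is losing the only planned test of tolerability against naltrexone, which could not support that conclusion anyway.
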